16. STUDY MEDICATION COMPLIANCE

Compliance to any study medication will be presented for the SAF analysis set.

The following compliance parameters will be summarized in tables:

- Treatment compliance (%) presented for both cycle 1 and full treatment period

16.1. DERIVATIONS

- Treatment compliance (%) = $(\text{actual cumulative dose} / \text{planned cumulative dose}) * 100$

Planned dose by cycle:

- Debio 1143 (mg): $20 * 200 = 4000$
- Nivolumab (mg): 480

Planned cumulative dose:

Document: T:\sas\Debiopharm\Debio_1143\CZA60507\Biostatistics\Documentation\SAP\SAP Text\V5

Author: XXXXXXXXXX Version Number: 5.0
 Version Date: 19APR2022

Template No.: CS_TP_BS016 Revision 5
 Effective Date: 01Apr2018

Reference: CS_WI_BS005

Copyright © 2009, 2010, 2012, 2016, 2018 IQVIA. All rights reserved. The contents of this document are confidential and proprietary to IQVIA Holdings Inc. and its subsidiaries. Unauthorized use, disclosure or reproduction is strictly prohibited.

- Debio 1143 (mg): Number of cycles started x Planned dose by cycle
- Nivolumab (mg): Number of cycles started x Planned dose by cycle

When Debio 1143 is ongoing, cycle starts if at least one dose of Debio 1143 > 0 is received on Day 1. Cycle period is defined from Day 1 of current cycle to day before Day 1 of the next cycle.

If Debio 1143 stopped but Nivolumab is ongoing, cycle period is defined as 28 days, continuing from the date of last Debio 1143 administration >0. (ie. For example, if last Debio 1143 administration is on 1APR21 corresponding to C4D17, next Nivolumab administration received on 14APR21 would correspond to C5D2).

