In the first-in-human phase I single-agent trial, Debio 1143 was well tolerated up to doses of 900 mg/d on Days 1-5 every 3 weeks (q3w) and up to 400 mg/d Days 1-14 q3w. The MTD was not reached for either of these schedules. The prolonged dosing schedule of Debio 1143 with a total cumulative dose of 5600 mg/cycle showed good tolerability, with an acceptable toxicity profile and treatment compliance, similar to the short-course regimen at the highest explored dose level (i.e., total cumulative dose of 4500 mg/cycle). PDy demonstration of target occupancy and linear PK were observed within the explored dose range, even at doses as low as 120 mg/d. High interpatient variability was seen, but without drug-accumulation. The dose of 200 mg/d was chosen as the RP2D when Debio 1143 was combined with both cisplatin-based chemo-radiation (100 mg/m^2 IV on Day 2 q3w) in patients with locally advanced SCCHN, and with carboplatin and paclitaxel q3w in patients with NSCLC, triple-negative breast cancer or ovarian cancer [cf. section 6.2.1.4.5 of Debio 1143 Investigator’s Brochure and (28)]. It is therefore expected that a Debio 1143 starting dose of 150 mg/d, given orally on Days 1-10 and Days 15-24 q4w, with a dose-intensity of 750 mg/week and a maximal cumulative dose of 3000 mg per cycle is tolerable, relevant in terms of biological target engagement and feasible as single agent and in combination with standard dose of nivolumab.

Given that a linear dose-effect response was not observed above 120 mg/d in the single agent mechanistic studies, and that no further PDy effects are expected when the Debio 1143 dose is increased, dose escalation beyond 200 mg/d is not planned in this study.

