1. INTRODUCTION

This document describes the rules and conventions to be used in the presentation and analysis of efficacy, safety, pharmacokinetic (PK), pharmacodynamic (PDy), and genetic data for Protocol Debio 1143-106. It describes the data to be summarized and analysed, including specifics of the statistical analyses to be performed.

This statistical analysis plan (SAP) is based on protocol version 4 dated 03rd April 2020. This SAP will cover analyses for both part A (phase 1b) and part B (phase 2).

Document:	T:\sas\Debiopharm\Debio_1143\CZA60507\Biostatistics\Documentation\SAP\SAP Text\V5	Version Number:	5.0
Author:	██████████	Version Date:	19APR2022

Template No.: CS_TP_BS016 Revision 5
Effective Date: 01Apr2018

Reference: CS_WI_BS005

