15.1. DERIVATIONS

- Duration of exposure (weeks)
 - Debio 1143: $(\text{date of last dose of Debio 1143} - \text{date of first dose of Debio 1143} + 1) / 7$
 - Nivolumab: $(\text{date of last dose of nivolumab} - \text{date of first dose of nivolumab} + 1) / 7$
- Actual Cumulative dose
 - Debio 1143 (mg): sum of the actual administered dose across all dosing dates
 - Nivolumab (mg): sum of the total dose administered across all cycles, if an infusion was interrupted then the total volume infused will be used to calculate the effective mg quantity administered ($\text{planned dose} \times (\text{total volume infused} / \text{total volume prepared})$)
- For every unique interruption, defined as any occurrence of a 0 mg dose succeeding a non-0 mg dose, the duration of unique Debio 1143 interruption = $(\text{date of last day with Debio 1143 exposure form completed with actual dose of 0 mg} - \text{date of first day with Debio 1143 exposure form completed with actual dose of 0 mg}) + 1$

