19.1. PHARMACOKINETIC CONCENTRATIONS

Individual PK blood sample collection times, derived sampling time deviations, and plasma concentrations of Debio 1143 and Debio 1143-MET1 and serum concentrations of nivolumab will be listed and figures will be presented for Cycle 1 Day 1. Time deviations will be calculated in reference to Debio 1143 administration or nivolumab infusion as specified in Table 8-1, Table 8-2, and Table 8-3 of protocol and taking into account the windows of tolerance specified in Table 8-5 of protocol.

Time deviations (actual sampling time outside the windows of tolerance specified in Table 8-5 of protocol) will be considered only relevant and a reason for data exclusion from PK analysis in case of pre-dose concentrations. All other post-dose time deviations will be considered not relevant and therefore concentrations will always be included in the PK analysis.

Should ADA samples be analyzed for serum ADA entities, results for nivolumab ADA will be listed, and ADA concentrations will be summarized only for ADA positive samples.

For each analyte, concentrations will be summarized using descriptive statistics (described in Section 7.6) by cycle, study day and scheduled time. In addition, the summaries for nivolumab concentrations will be stratified by Nivolumab regimen (240 mg or 480 mg) as applicable and summaries for Debio concentrations will be stratified by Debio regimen (150 mg or 200 mg).

Concentrations that are missing will be omitted from the calculation of descriptive statistics.

To derive PK parameters and for summary statistics (except for calculations involving logarithmic transformations), concentrations reported as BLQ will be considered as 0 when they occur before the first quantifiable concentration. BLQ concentrations occurring after the first quantifiable concentration will be set to 1/2 LOQ.

For summary statistics where calculation involves logarithmic transformations (including geometric mean calculation), plasma levels BLQ will be set to 1/2 LOQ.

Document: T:\sas\Debiopharm\Debio_1143\CZA60507\Biostatistics\Documentation\SAP\SAP Text\V5

Author: XXXXXXXXXX Version Number: 5.0
Version Date: 19APR2022

Template No.: CS_TP_BS016 Revision 5
Effective Date: 01Apr2018

Reference: CS_WI_BS005

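### SAP 16.1 measures Debio 1143 compliance against 4000 mg per cycle for every patient, so a fully adherent Part A patient at 150 mg/day is reported at 75% in Cycle 1

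*SAP*

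**What the plan says.** SAP 16.1 defines "Treatment compliance" as 100 times actual cumulative dose over planned cumulative dose. For Debio 1143 the planned dose per cycle is a single figure, 20 x 200 = 4000 mg, and the denominator is "Number of cycles started x Planned dose by cycle". No exception is made for Part A or for dose level 1. The numerator, in SAP 15.1, is the "sum of the actual administered dose across all dosing dates".

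Part A is within the scope of this derivation:

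- SAP section 1: "This SAP will cover analyses for both part A (phase 1b) and part B (phase 2)".
- SAP section 16: "Compliance to any study medication will be presented for the SAF analysis set", for Cycle 1 and for the full treatment period. The safety set in SAP 6.3 is every enrolled patient with at least one dose of either drug.
- SAP section 9 has outputs produced separately for each part, with Part A shown overall and by dose level.

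Dose level 1 is 150 mg/day on Days 1-10 and 15-24 (protocol Table 5-2; SAP 4.1.1). Protocol 5.3 describes that regimen "with a dose-intensity of 750 mg/week and a maximal cumulative dose of 3000 mg per cycle".

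**The concern.** The denominator is the planned dose at 200 mg/day, but it is applied to patients planned for 150 mg/day. Their reported percentage falls short of 100% however well they adhere. In a table by dose level, the lower dose would appear to have the worse compliance, and a reader of the study report could take that for poorer adherence or tolerability at 150 mg. The Part A overall column would average percentages measured against the right target with percentages measured against the wrong one.

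Nothing suggests that a common 200 mg reference was intended. The result is labelled compliance, not relative dose intensity. SAP 4.3, which lists changes from the protocol, does not mention such a reference. Elsewhere the SAP keeps the two regimens apart: in SAP 19.1, "summaries for Debio concentrations will be stratified by Debio regimen (150 mg or 200 mg)". The nivolumab figure of 480 mg per cycle fits both permitted schedules (2 x 240 or 1 x 480), so only the Debio 1143 line has the problem.

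**Working it through.** Inputs:

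- Dosing days per cycle: 10 + 10 = 20 (protocol Table 5-1).
- Daily dose: 150 mg at dose level 1, 200 mg at dose level 2 (protocol Table 5-2).
- SAP denominator: 4000 mg per cycle started (SAP 16.1).

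**The plan's own figures.** 20 x 200 = 4000 mg reproduces SAP 16.1 and is right at 200 mg/day. 20 x 150 = 3000 mg reproduces the figure in protocol 5.3 for the starting dose.

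**Cycle 1.** Reported compliance = 100 x (doses taken x daily dose) / 4000. Against the assigned level it would be 100 x (doses taken x daily dose) / (20 x daily dose).

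| Doses taken | 150 mg, as SAP 16.1 | 150 mg, assigned level | 200 mg, either way |
|---|---|---|---|
| 20 of 20 | 3000/4000 = 75.0% | 3000/3000 = 100% | 100% |
| 18 of 20 | 2700/4000 = 67.5% | 2700/3000 = 90% | 90% |
| 14 of 20 | 2100/4000 = 52.5% | 2100/3000 = 70% | 70% |

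The shortfall is a factor of 0.75, not a constant: 25 points at full adherence, 22.5 at 18 of 20 and 17.5 at 14 of 20.

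**Full treatment period.** For a fully adherent patient with k of n cycles at 150 mg and the rest at 200 mg, reported compliance = 100 x (k x 3000 + (n - k) x 4000) / (n x 4000).

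- k = n (no switch): 75%.
- k = 2, n = 4: 14000/16000 = 87.5%.
- k = 3, n = 13: 49000/52000 = 94.2%.

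The overall figure thus lies between 75% and 100% for a switched patient, while that patient's Cycle 1 figure stays at 75%.

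**Part A overall column.** The final count per dose level is not in the documents, so two illustrative splits within the planned 3 to 12 evaluable patients are used. All patients are taken as fully adherent, and the values are Cycle 1.

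- 3 at 150 mg and 6 at 200 mg: (3 x 75 + 6 x 100)/9 = 91.7%.
- 6 and 6: (6 x 75 + 6 x 100)/12 = 87.5%.

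Both should be 100%.

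**The case against.** The formula is not in dispute. The objection is that little depends on it, and most of that stands.

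- **Dose selection.** A reader might infer that the ratio could have tilted the choice of recommended phase II dose, because the Part A primary objective names treatment compliance. The documents do not support this. Escalation follows DLT counts under 3+3 (SAP 4.1.1). The supporting material is patient profiles built from raw data (SAP 5.1), and SAP 5.2 sends only those profiles to the monitoring committee in Part A. The compliance table belongs to the final analysis. SAP version 5.0 already records the futility of the Part B cohorts (SAP 4.3), so the dose had been chosen by then. The endpoint lists (protocol 8.1.2, SAP 3.2) also use treatment compliance to mean discontinuations and modifications, which this denominator does not touch.
- **The 70% rule.** A reader might see 67.5% for a patient with 18 of 20 doses and conclude that the patient fails the exposure criterion. SAP 6.2 spells that criterion out as at most 6 missed doses. No rule compares it with the SAP 16.1 ratio.
- **A uniform 0.75 factor.** It is tempting to apply this to every dose-level-1 value. It does not hold for the overall figure of a patient switched to 200 mg, which SAP 4.1.1 permits if that is the recommended dose.
- **Visibility.** Few patients are involved, the table is descriptive, and the exposure tables in SAP section 15 show the number of administrations. An attentive reader could see 20 administrations beside 75%.

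These points limit the consequence. They do not make the percentage correct, and a reader should not have to decode it from another table.

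**Conclusion.** The point holds as a reporting error of minor to moderate weight. As written, SAP 16.1 understates Debio 1143 compliance for patients assigned to 150 mg/day. The factor is 0.75 in Cycle 1 and throughout for those who stay at 150 mg, with a smaller understatement overall for those moved to 200 mg. The Part A comparison by dose level carries a gap of 25 points at full adherence that has nothing to do with adherence, and the overall column is not on one scale.

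No DLT status, analysis set, 3+3 decision, dose selection or efficacy result changes.

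The conclusion assumes that the compliance table is programmed as SAP 16.1 reads and that Part A is included, as SAP sections 1, 9 and 16 state. The upper part of the 75% to 100% range assumes that switched patients moved to 200 mg. The documents do not state the chosen dose, though the fixed 20 x 200 in SAP 16.1 suggests it.

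**What to change.** In SAP 16.1, replace the single 4000 mg figure with 20 times the dose level assigned for that cycle: 3000 mg at dose level 1 and 4000 mg at dose level 2. For a Part A patient switched to the recommended dose, use the new level from the cycle of the switch. Planned cumulative dose then becomes the sum over cycles started of each cycle's planned dose. The nivolumab line needs no change. Rerun the Part A compliance table.

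The cost is one SAP line and one table rerun. Only an analysis denominator changes.

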17. EFFICACY OUTCOMES

17.1. PRIMARY EFFICACY

For the purposes on the analyses described below, PD could be clinical progression (as recorded on the “End of Treatment” eCRF) or radiological progression (as recorded on the “overall response – RECIST v1.1” eCRF). In case of premature discontinuation with SD at the end of study (EOS) visit, this SD will be included in the derivation of the categorical efficacy parameters only if the assessment has been performed at least 35 days after treatment start.

17.1.1. PRIMARY EFFICACY VARIABLE & DERIVATION

The primary efficacy variable is confirmed ORR as per RECIST v1.1 and/or CGIG criteria (cohort 4, if applicable).

Confirmed objective response as per RECIST v1.1 is a confirmed best overall response (cBOR) of partial response (PR) or complete response (CR). The full derivation of confirmed BOR is included in Section 17.2.1.2.

In the situation of lack of RECIST evaluation data (cohort 4 only), confirmed objective response as per GCIG criteria will be done using CA-125 levels. Patients will be scored as having attained a CA-125 response if they meet the GCIG-Rustin-modified criteria which require that there is at least a 50% reduction in CA-125 levels from a pre-treatment sample. The response must be confirmed and maintained for at least 28 days. Patients can be evaluated according to CA-125 only if they have a pre-treatment sample that is at least twice the upper limit of normal and within 2 weeks prior to starting treatment.

Document: T:\sas\Debiopharm\Debio_1143\CZA60507\Biostatistics\Documentation\SAP\SAP Text\V5

Author: [REDACTED] Version Number: 5.0
Version Date: 19APR2022

Template No.: CS_TP_BS016 Revision 5
Effective Date: 01Apr2018

Reference: CS_WI_BS005

17.1.2. MISSING DATA METHODS FOR PRIMARY EFFICACY VARIABLE

No imputation methods will be used for the primary efficacy variable. If there is lack of available tumour assessment data due to treatment failure, then the patient will have a cBOR of not evaluable (NE).

17.1.3. PRIMARY ANALYSIS OF PRIMARY EFFICACY VARIABLE

Due to the exploratory nature of the trial, there will be no formal hypotheses testing. The primary efficacy analysis will be performed for the EFF analysis set.

At the final analysis for part B, a homogeneity Fisher exact test with a significance level of 0.3 will be conducted in the non-futile cohorts showing a confirmed response rate of at least 15% (≥ 4 responders). If the primary endpoint homogeneity assumption is confirmed, the estimated confirmed ORR will be reported overall and by cohort based on the posterior beta distribution with a two-sided 95% credibility interval. Otherwise, if the homogeneity test does not reach significance level of 0.3, the estimated confirmed ORR and two-sided 95% credibility interval will be similarly reported in each cohort separately.

The efficacy of the futile cohorts and the cohorts with less than 15% confirmed response rate will be reported separately.

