**Table 11-3 Boundaries for declaring efficacy**

# Patients (inclusive)	# Responses (inclusive) are considered efficacious	Actions
15	4   5   6   7   8   9   10   11   12   13   14   15	Claim efficacy

At the final analysis, a homogeneity Fisher exact test with a significance level of 0.3 will be conducted in the non-futile cohorts showing a response rate of at least 15%. If the primary endpoint homogeneity assumption is confirmed, it will be reported in the pooled cohorts as the absolute and relative frequencies with a one-sided exact binomial confidence interval at an alpha level of 0.05. Otherwise, the confirmed ORR will be similarly reported in each cohort separately.

The efficacy of the futile cohorts and of the cohorts with a confirmed response rate lower than 15% will be reported separately.

ORR, BOR and DCR will be presented using contingency tables with absolute and relative frequencies. Time-to-response, DOR, PFS and OS medians and rates will be determined using the Kaplan-Meier method.

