2.1.2. PART B

The primary objective of the basket trial is to evaluate the preliminary anti-tumour activity of Debio 1143 at the RP2D in combination with nivolumab at the standard dose, overall and in each patient cohort.

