9. OUTPUT PRESENTATIONS

Appendix 1 shows conventions for presentation of data in outputs.

The templates provided with this SAP describe the presentations for this study and therefore the format and content of the summary tables, figures, and listings to be provided by IQVIA Biostatistics.

All endpoints such as demographics, baseline characteristics, safety, PK, PDy, etc. will be presented overall and by dose level for Part A and cohort for Part B.

All outputs will be presented for both Part A and Part B separately.

For Part B, the efficacy outputs will be reported by cohort.

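### SAP 17.1.3 equates a 15% confirmed response rate with 4 responders, which in a cohort of 15 it is not, and its by-cohort-only clause contradicts the sentence before it

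*SAP*

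**What the plan says.** The Part B objective in SAP 2.1.2 is anti-tumour activity of the combination "in combination with nivolumab at the standard dose, overall and in each patient cohort". SAP 17.1.3 sets out when an overall figure is produced:

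- A Fisher exact test of homogeneity at level 0.3 is run only in cohorts that were not futile and that pass a response gate, worded as "showing a confirmed response rate of at least 15% (≥ 4 responders").
- The first branch gives the overall figure: "If the primary endpoint homogeneity assumption is confirmed, the estimated confirmed ORR will be reported overall and by cohort".
- The second branch does not: "Otherwise, if the homogeneity test does not reach significance level of 0.3", the estimate and its credibility interval are given for each cohort separately.
- Futile cohorts and "the cohorts with less than 15% confirmed response rate will be reported separately".

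Protocol 11.6.4.3 has the same test and level. There the test "will be conducted in the non-futile cohorts showing a response rate of at least 15" per cent, with no responder count attached. If homogeneity is confirmed, the endpoint is reported in the pooled cohorts. "Otherwise, the confirmed ORR will be similarly reported in each cohort separately". Protocol 11.6.2 and 11.6.4 give the same direction: pool when rates are homogeneous, otherwise report by cohort.

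Four responses of 15 appears in the protocol (11.1, 11.6.4 and Table 11-3) as a different rule, the boundary for claiming first proof of efficacy in a cohort. For the ORR analysis, SAP 4.3 declares only the change to a posterior estimate with a credibility interval.

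**The concern.** The bracketed count reads as a translation of 15% into responders, but it does not match 15% at the planned cohort size. It appears to carry the efficacy boundary into the pooling gate. The percentage and the count then give different sets of cohorts to test and pool, and a cohort with 3 of 15 belongs to neither reporting group.

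The last branch has a separate fault. A homogeneity test that does not reach its significance level has failed to reject homogeneity, and that is the result on which the preceding sentence calls for an overall estimate. The two sentences therefore send the same result in opposite directions.

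What is at stake is whether an overall confirmed ORR is reported for the primary endpoint, and which cohorts enter it. SAP 17.1.4 repeats the same analysis on the ITT/Safety set, so the fault carries over to the sensitivity analysis.

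**Working it through.** **Inputs.** Maximum 15 evaluable patients per cohort; futility looks on unconfirmed responses, continuing with at least 1 of 8 and then at least 2 of 11; prior Beta(0.5, 0.5); efficacy threshold 0.80; confirmed reference rate 0.15 (SAP 5.3; protocol 11.6.3 and 11.6.4). Protocol Table 11-1 prints 0.17 for the confirmed rate, so both values are tried. The assumed rates are 15% confirmed and about 17% unconfirmed (SAP 5.3).

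**Where 4 comes from.** With r responses in 15, the posterior is Beta(0.5 + r, 15.5 − r).

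| r/15 | Prob(θ > 0.15) | Prob(θ > 0.17) |
|---|---|---|
| 3 | 0.726 | 0.647 |
| 4 | 0.892 | 0.843 |

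Against 0.80, the efficacy boundary is 4 under either reference rate. The plan's figure is reproduced, but as the efficacy rule.

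**What 15% gives.** 0.15 × 15 = 2.25, so the smallest count is 3 (3/15 = 20.0%); 2/15 = 13.3% fails and 4/15 = 26.7% is well above. Four is the smallest count reaching 15% only for n = 21 to 26 (0.15 × 21 = 3.15; 0.15 × 26 = 3.9), sizes that no cohort can reach.

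**How often it matters.** Exact enumeration of the 8/11/15 design, with independent patients, every confirmed response also an unconfirmed one, and unconfirmed rate = confirmed rate × 17/15. Let q be the probability that a cohort is non-futile and meets the gate. The excluded share is P(non-futile, exactly 3/15) divided by q with cut-off 3. The chance that at least two of four equally active cohorts qualify is 1 − (1 − q)⁴ − 4q(1 − q)³.

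| True confirmed rate | exactly 3/15 | q, cut-off 3 | q, cut-off 4 | excluded share | at least 2 of 4: cut-off 3 v 4 |
|---|---|---|---|---|---|
| 15% | 0.186 | 0.358 | 0.172 | 52% | 45% v 14% |
| 20% | 0.216 | 0.560 | 0.344 | 39% | 77% v 43% |
| 25% | 0.198 | 0.728 | 0.530 | 27% | 94% v 73% |
| 30% | 0.152 | 0.847 | 0.695 | 18% | 99% v 91% |

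Rows below the first assume that the 17/15 ratio holds at higher rates. At 15% confirmed, varying the unconfirmed rate from 15% to 20% moves the excluded share only from 51% to 53%.

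**Effect on an overall estimate.** It depends on the counts (non-futile cohorts of 15, exact test):

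- 3, 4, 5: under the 15% gate p = 0.91 and the overall ORR is 12/45 = 26.7%. Under the 4-responder gate, 4 and 5 are pooled: 9/30 = 30.0%.
- 3, 4: the 15% gate pools 7/30 = 23.3%. The 4-responder gate leaves one cohort and nothing to pool.
- 3, 7, 8: under the 15% gate p = 0.16, so there is no overall ORR. Under the 4-responder gate, 7 v 8 gives p = 1.00 and an overall ORR of 15/30 = 50.0%.
- No cohort with exactly 3: no difference.

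**The branch.** Two cohorts with 4 and 6 of 15 give p = 0.70, and homogeneity is not rejected. The protocol and the first SAP sentence report overall and by cohort; the next SAP sentence, read literally, reports by cohort only. With 4 and 8 of 15, p = 0.26 and homogeneity is rejected at 0.3. The protocol reports by cohort only; in the SAP, neither stated condition is met. So a non-significant test meets both conditions and a significant one meets neither.

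**The case against.** The strongest reply is that the rule may have no cohorts to act on. The test applies only to non-futile cohorts, and SAP 4.3 gives futility of the Part B cohorts as its reason for not pooling Parts A and B. It does not say that every cohort was futile, so this is not proof, but it is the natural reading. The trial is also exploratory with no formal hypothesis testing, and the efficacy claim is made cohort by cohort. All of this stands and limits the weight of the point.

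On the branch, one can say that the sentence opens with a word that already covers homogeneity not being confirmed, and that a loose reading (the p-value falls short of 0.3) restores the protocol's rule. That shows the intent, but it is not what failing to reach a significance level normally means.

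On the count, protocol 11.6 leaves the definitive analysis to the SAP, so a stricter gate is permissible. The defect is presenting 4 as the equivalent of 15%, leaving 3/15 without a group, and not listing the change in 4.3.

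The probabilities also have limits. They assume that every non-futile cohort reaches 15 and that all four are equally active. Two cohorts qualifying does not ensure an overall ORR, which also needs p of at least 0.3. Protocol 5.1.2 allows a cohort to stop for poor accrual, so a cohort may be smaller than 15.

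**Conclusion.** Both errors are real, and the point is minor. The 4-responder count is not the 15% criterion in a cohort of 15, and it narrows the protocol's gate without declaration. On the stated assumptions it excludes 52% of qualifying cohorts at a true confirmed rate of 15%, falling to 18% at 30%. The by-cohort-only clause contradicts the sentence before it and the protocol.

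A reader might infer three stronger things that the documents do not support:

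- That the SAP deliberately reverses the protocol's pooling rule. The preceding sentence agrees with protocol 11.6.2, 11.6.4 and 11.6.4.3, so this is a wording error with a known intended direction.
- That the narrower gate always raises the overall estimate. It can raise it, remove it, create one that the protocol's gate would not report, or leave it unchanged.
- That SAP section 9 rules out an overall result because it says "For Part B, the efficacy outputs will be reported by cohort". That is a general presentation statement, 17.1.3 is the specific rule, and protocol 11.6 itself exempts futile cohorts and heterogeneous efficacy data from overall reporting.

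Per-cohort estimates and efficacy claims are unaffected.

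**What to change.** In SAP 17.1.3, state the two branches by p-value: if p ≥ 0.3, report overall and by cohort; if p < 0.3, report by cohort only.

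Delete the bracketed responder count, so that the gate is an observed confirmed rate of at least 15% at whatever number of evaluable patients the cohort has. If 4 responders is what the sponsor intends, keep it as a rule in its own right, list it in SAP 4.3 as a change from the protocol, and say how a non-futile cohort with 3/15 is reported.

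The cost is a wording edit in one section, plus one line in 4.3 if the count stays. It needs no new data or analysis.
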